4.5.3.2 Abnormal Liver Enzymes and Liver Function Values

Summaries of abnormal liver enzymes and liver function tests post-baseline will be presented for ALT, AST, Direct Bilirubin, Total Bilirubin, and ALP. All scheduled and unscheduled results will be included in these analyses.

4.5.4 Vital Signs

The number and percentage of subjects with abnormally low or high vital sign values postbaseline based on the normal ranges defined in Table 3 will be presented. All scheduled and unscheduled results will be included in this analysis.

Measurement	Normal Range
Body mass index	$18 - 35 \text{ kg/m}^2$
Temperature	95-100 °F (35-37.8 °C)
Diastolic blood pressure	60 – 90 mmHg
Systolic blood pressure	90 – 140 mmHg
Heart rate	50 – 100 bpm
Respiration rate	10-25 breaths per minute

Table 3 Vital Signs Normal Ranges

A listing of subjects with abnormalities in vital sign parameters will be presented.

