#### **Duration of Subject's Participation:**

For subjects who follow **SCHEDULE 'A'**, the total study duration per subject, from Visit 1 to Visit 22/EOS will be up to ~156 weeks (3 years) or until SPN-812 becomes approved and commercially available for Adults.

For subjects who follow **SCHEDULE 'B'**, the total study duration per subject is up to 160 weeks, including screening (up to 4 weeks) and from Visit 1 to Visit 22/EOS (up to ~156 weeks [3 years]), or until SPN-812 becomes approved and commercially available for Adults.

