# 2.3. Primary Safety Endpoints

The primary safety endpoints are adverse events (AEs), clinical safety laboratory test results, vital signs, weight, electrocardiograms (ECGs), physical examination, and the Columbia Suicide Severity Rating Scale (C-SSRS).

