# 3.3.3.1. Inclusion Criteria 'B':

- 1. Is male or female, aged 18 to  $\leq$  65 years at screening.
- 2. Is able to read and understand the Informed Consent Form (ICF).
- 3. Written informed consent obtained from the subject (a signed ICF).
- 4. Weight within the normal or overweight ranges according to accepted values of the Body Mass Index (BMI) Chart (18.0 to 35.0 kg/m^2).
- 5. Is able to swallow capsules whole, without crushing, chewing or cutting.
- 6. Is willing and able to attend study appointments within the specified time windows.
- 7. Has a primary diagnosis of ADHD according to the DSM-5 classification, with diagnosis made at least 6 months prior to screening and confirmed with Structured Clinical Interview for DSM-5 Clinical Trials version (SCID-5-CT; *de novo* subjects).
- 8. Has an AISRS total score of  $\geq$  24 at the screening (Visit 'S').
- 9. Has a CGI-S score of  $\geq$  4 (mildly ill or worse) at the screening (Visit 'S').

- 10. Females of childbearing potential (FOCP) must be either sexually inactive (abstinent) or, if sexually active, must agree to use one of the following acceptable birth control methods beginning at least 28 days prior to the first dose of SM and throughout the study:
  - a. Simultaneous use of male condom and intra-uterine contraceptive device placed at least 4 weeks prior to first SM administration
  - b. Surgically sterile male partner
  - c. Simultaneous use of male condom and diaphragm with spermicide
  - d. Established hormonal contraceptive

Females are considered not to be of childbearing potential if they are either postmenopausal (amenorrhea for at least 2 years and serum follicle stimulating hormone [FSH] level of >40 IU/L) or permanently sterilized (e.g., bilateral tubal ligation, hysterectomy, bilateral oophorectomy for 6 months minimum prior to screening).

- 11. Males must:
  - a. Use 2 methods of contraception in combination if his female partner is of childbearing potential; this combination of contraceptive methods must be used from Visit 1 (baseline) to ≥ 1 month after the last dose of SM; or
  - b. Have been surgically sterilized prior to the Screening Visit.

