### 7.9. Safety Analysis

Safety analyses will be performed by optimized dose group and overall based on the Safety Population.

The incidence rate of AEs will be calculated for each system organ class (SOC) and preferred term (PT). The severity of the AEs and the relationship to SM will be summarized for each SOC and PT.

AEs will be summarized using discrete summaries at the subject and event level by SOC and PT, and by severity and relationship separately. Verbatim description and Medical Dictionary for Regulatory Activities (MedDRA) SOCs and PTs for all AEs will be contained in the subject data listings.

Clinical laboratory values will be summarized by visit by optimized dose group and overall using descriptive statistics. For quantitative laboratory parameters, both actual values and change from baseline values will be summarized.

Vital signs will be summarized by visit by optimized dose group and overall using descriptive statistics. Both actual values and change from baseline will be summarized.

ECG results will be summarized by visit by optimized dose group and overall using descriptive statistics (for quantitative ECG parameters) and frequency tables (for qualitative ECG parameters, including the overall ECG finding).

C-SSRS outcomes will be summarized using number and percent of subjects by categories for suicidal ideation only, suicidal behavior only and suicidality (ideation and behavior combined). The summary will be presented by optimized dose group and overall.

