2.6.4 Vital Signs

Vital signs data will include weight (kg), BMI (kg/m²), systolic blood pressure (mmHg), diastolic blood pressure (mmHg), heart rate (beats per minute), respiratory rate (breaths per minute) and temperature (°C). Blood pressure and heart rate measurements taken in the standing and the seated position will be analyzed.

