5.1 List of Tables

Number	Title
Table 1.1	Subject Disposition – All Subjects
Table 1.2	Protocol Deviations and Violations – All Subjects
Table 2.1	Demographic and Baseline Characteristics - Safety Population
Table 2.2	Prior Medications by ATC Class Level 4 and Preferred Name - Safety Population
Table 2.3	Concomitant Medications by ATC Class Level 4 and Preferred Name – Safety Population
Table 2.4	Medical History by System Organ Class and Preferred Term – Safety Population
Table 3.1	Study Drug Exposure by Age Group - Safety Population
Table 3.2	Planned Doses by Study Visit and Age Group - Safety Population
Table 3.3	Study Drug Exposure by Age Group and Actual Dose - Safety Population
Table 4.1	Overview of Treatment-emergent Adverse Events - Safety Population
Table 4.2	Treatment-emergent Adverse Events by System Organ Class and Preferred Term - Safety Population
Table 4.3	Treatment-emergent Adverse Events Occurring in at Least 5% of Subjects by Preferred Term - Safety Population
Table 4.4	Treatment-emergent Adverse Events by System Organ Class, Preferred Term, and Maximum Severity - Safety Population
Table 4.5	Treatment-emergent Adverse Events by System Organ Class, Preferred Term, and Relationship to Study Drug - Safety Population
Table 4.6	Serious Treatment-emergent Adverse Events by System Organ Class and Preferred Term - Safety Population
Table 4.7	Treatment-emergent Adverse Events Leading to Study Drug Discontinuation by System Organ Class and Preferred Term - Safety Population
Table 4.8	Treatment-emergent Adverse Events of Special Interest by System Organ Class and Preferred Term - Safety Population
Table 5.1.1	Subjects with Potentially Clinically Significant Post-Baseline Hematology Results – Safety Population
Table 5.1.2	Change from Baseline in Hematology Parameters by Study Visit – Safety Population
Table 5.2.1	Subjects with Potentially Clinically Significant Post-Baseline Chemistry Results – Safety Population
Table 5.2.2	Change from Baseline in Chemistry Parameters by Study Visit – Safety Population
Table 5.3	Subjects with Abnormal Liver Enzymes and Liver Function Tests – Safety Population
Table 5.4	Change from Baseline in Urinalysis Parameters by Study Visit – Safety Population
Table 6.1	Vital Signs by Study Visit – Safety Population

Supernus Pharmaceuticals, Inc. CONFIDENTIAL

Number	Title
Table 6.2	Subjects with Abnormalities in Vital Signs Parameters - Safety Population
Table 7.1	12-Lead Electrocardiogram by Study Visit – Safety Population

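### SAP 4.5.4 sets no count of within-subject weight change from measured weights; its only weight-related threshold is a fixed BMI range that ignores baseline

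*SAP*

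**What the plan says.** Protocol 2.3 lists the primary safety endpoints as adverse events, "clinical safety laboratory test results, vital signs, weight, electrocardiograms (ECGs), physical examination" and the C-SSRS, so weight stands beside vital signs as a separate item. Protocol 5.1.1 to 5.1.5 schedule weight at every clinic visit. Under Schedule A, participation lasts "up to ~156 weeks (3 years) or until SPN-812 becomes approved and commercially available for Adults".

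SAP 2.6.4 puts weight in kg and BMI into the vital-sign data. SAP 4.5.4 then gives one counting rule, "The number and percentage of subjects with abnormally low or high vital sign values", applied to post-baseline results, scheduled and unscheduled, against Table 3. The BMI row of Table 3 is 18-35 kg/m². There is no row for weight or for change in weight.

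The same numbers, 18.0 to 35.0 kg/m², form the Schedule B entry limit in Protocol 3.3.3.1, item 4 ("Weight within the normal or overweight ranges according to accepted values of the Body Mass Index (BMI) Chart"). Criteria A (Protocol 3.3.2) state no BMI limit.

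For vital signs Protocol 7.9 says: "Both actual values and change from baseline will be summarized". The SAP's by-visit table, Table 6.1, is titled "Vital Signs by Study Visit – Safety Population". The hematology, chemistry and urinalysis tables in the same list (5.1.2, 5.2.2 and 5.4) carry change from baseline in their titles. SAP 4.5.5 defines within-subject change categories for QT and QTcF.

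**The concern.** Slow weight change is a safety outcome that a study of this length can show and a short trial cannot. The question for such an outcome is how many subjects lost or gained a substantial share of their starting weight. A fixed BMI range answers a different one: how many were ever below 18 or above 35. A subject in the middle of the range can change a great deal and still be classed as normal, while a subject near or beyond an edge can be classed as abnormal after little or no change.

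The protocol's background gives some reason to look. Decreased appetite is among the most common adverse events in the summaries of 812P201, 812P202, 812P301, 812P303, 812P302 and 812P304. Five of these six studies are pediatric, and the adult one (812P201) used the immediate-release product in 26 subjects per treatment. None of the summaries names a weight-change event. This supports a prespecified look at weight; it does not show that there is a weight problem.

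**Working it through.** The plan gives no figure on weight change, so there is nothing of its own to reproduce.

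**Inputs.** Limits 18 and 35 kg/m² (SAP Table 3). Height is taken as fixed, so percent change in BMI equals percent change in weight; Protocol 5.1.2 to 5.1.5 do not list height among the procedures at Visits 2 to 22.

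**Change needed before a subject is counted.** Loss must exceed 1 − 18/BMI₀; gain must exceed 35/BMI₀ − 1.

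| Starting BMI | Loss | Gain |
|---|---|---|
| 22 | 1 − 18/22 = 18.2% | 35/22 − 1 = 59.1% |
| 26 | 1 − 18/26 = 30.8% | 35/26 − 1 = 34.6% |
| 30 | 1 − 18/30 = 40.0% | 35/30 − 1 = 16.7% |

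In kilograms, at an assumed height of 1.75 m (1.75² = 3.0625), BMI 26 is 79.6 kg. The limits are 18 × 3.0625 = 55.1 kg and 35 × 3.0625 = 107.2 kg.

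**Starting BMI from which a given change is counted.** A loss of p is counted only if BMI₀ < 18/(1 − p), and a gain of p only if BMI₀ > 35/(1 + p).

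- p = 7%: below 18/0.93 = 19.35, or above 35/1.07 = 32.71.
- p = 10%: below 18/0.90 = 20.00, or above 35/1.10 = 31.82.

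**Share of changes counted.** This needs a baseline BMI distribution, which the documents do not give. Five were assumed on 18-35: uniform, and truncated normal with mean/SD 25/4, 27/4, 28/4.5 and 30/4. The chance of a change was taken not to depend on starting BMI. The table gives the range over the five.

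| Change | Losses counted | Gains counted |
|---|---|---|
| 7% | 0.3-8.0% | 2.2-16.1% |
| 10% | 0.5-11.8% | 4.0-24.5% |
| 15% | 1.4-18.7% | 8.5-39.3% |
| 20% | 3.3-26.5% | 14.9-53.4% |

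More than half of the changes go uncounted in every case except a 20% gain with assumed mean BMI 30, where 53.4% are counted.

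**The opposite error.** A subject entering at BMI 34.9 is counted after a gain of more than 35/34.9 − 1 = 0.3%. A Schedule A subject already outside 18-35 is counted at the first post-baseline visit with no change at all.

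**The case against.** A reader might infer that large weight changes are never counted. The documents do not support that. SAP 4.5.1 treats every adverse event as treatment-emergent, and the title of Table 4.2 carries no 5% cut-off, so a weight change that an investigator reports is counted under its preferred term. Because SAP 2.6.4 makes weight part of the vital-sign data, it also belongs in Table 6.1 and Listing 6.1. What stands is narrower. The SAP sets no weight threshold for reporting an event. The by-visit summaries use observed data only (SAP 3.3), so they describe the subjects still attending and do not say how many individuals changed by a given amount.

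A reader might also infer that the SAP has dropped the change-from-baseline summary for vital signs. That would rest on a table title. SAP 3.2 defines a baseline for all safety assessments, the laboratory text in SAP 4.5.3 is equally silent on by-visit change, and the Appendix B shells that fix table content were not available. In addition, Protocol 7.9 speaks of vital signs and does not name weight. The text supports a request to state the content of Table 6.1, not a finding that something was removed.

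Nor does the BMI count merely reflect starting values. Schedule B subjects must be within 18.0-35.0 at screening, so for them a later value outside the range is essentially a crossing after entry. Criteria A allow a start outside the range, but those subjects first met the entry criteria of 812P306, which are not among the documents. How many are affected is unknown.

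**Conclusion.** The point holds as a gap in the prespecified counts. For a primary safety endpoint, the SAP has no number and percentage of subjects with a given weight change based on measured weights. The one threshold it has ignores baseline and, for most starting values, requires very large changes. The per-subject figures are exact given fixed height.

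That most large changes go uncounted is not established as fact. It depends on the baseline BMI distribution and on what is called large, and the documents give neither. It held under the distributions tried, with the one exception shown. Confidence is high on the missing count and low on whether Table 6.1 lacks change from baseline. The SAP should be amended on this point, but the gap does not undermine the study.

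**What to change.** Keep the BMI 18-35 row, which still shows subjects crossing a fixed limit. Add to SAP 4.5.4 and Table 6.2 the number and percentage of subjects with prespecified percent weight loss and percent weight gain from the SAP 3.2 safety baseline, at any post-baseline visit and by visit. Cut-offs of at least 7% and at least 10% in each direction are examples chosen for this review and have no source in the documents; the sponsor should choose and justify its own. SAP 4.5.5 already uses this form for QT and QTcF.

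State in SAP 4.5.4 that Table 6.1 includes change from baseline for weight and the other vital signs, in line with Protocol 7.9. This matters because Protocol 7.1 lets the SAP supersede the protocol's methods.

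The cost is some SAP wording and a few table rows. No new data are needed. More subjects will be flagged, and some of those changes will be unrelated to treatment, which an uncontrolled study cannot separate.

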4.5.5 ECG Data

Twelve-lead ECGs will be collected. Descriptive summaries will be presented for heart rate (bpm), PR interval (msec), QRS duration (msec), uncorrected QT interval (msec), and QTcF (msec).

Normal, abnormal but not clinically significant, and abnormal and clinically significant ECG investigator interpretation results will be summarized and flagged in the listings.

The number and percentage of subjects with post-baseline abnormally low or high values for heart rate, PR interval, and QRS duration based on the normal ranges defined in Table 4 will be presented.

Table 4	ECG Normal Ranges	

Parameter	Low	High
Heart Rate (beats/min)	45	120
PR Interval (msec)	120	220
QRS Duration (msec	80	130

Additionally, the number and percentage of subjects with actual QT and QTcF values \leq 450 msec, 450 msec to \leq 480 msec, 480 to \leq 500 msec, >500 msec and with changes from baseline \leq 30 msec, 30 msec to \leq 60 msec, and >60 msec will be presented.

All ECG results will be displayed in the data listings.

4.5.6 C-SSRS Data

C-SSRS outcomes will be summarized and listed. The number and percentages of subjects with a response of "Yes" at any visit by categories for suicidal ideation only, suicidal behavior only, suicidality (ideation and behavior combined) items, and non-suicidal self-injurious behavior will be presented.

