# 6.4. Treatment-Emergent Suicidal Ideation

Prospective assessment of suicidal ideation and suicidal behavior is a mandatory part of the safety evaluations for any drug developed for a psychiatric indication (FDA, 2012). In this study, the initial evaluation of subjects will be conducted prior to enrollment to assess lifetime suicidal ideation and to identify subjects who must not participate in the trial due to pre-existing suicidality risk. The assessment will then be repeated at each subsequent study visit to monitor the occurrence of new suicidal and self-injurious tendencies.

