# 6.4.1. Columbia Suicide Severity Rating Scale (C-SSRS)

Assessment of suicidal ideation and behavior will be conducted using the Columbia-Suicide Severity Rating Scale (C-SSRS) (Posner et al., 2011). The C-SSRS is an FDArecommended prospective assessment instrument that directly classifies suicidal ideation and behavior events into 11 preferred categories, including 5 levels of suicidal ideation, 5 levels of suicidal behavior, and the category of self-injurious behaviors with no suicidal intent. The C-SSRS "Baseline/Screening" version should only be administered at Visit 'S' to subjects who follow **SCHEDULE 'B'**. The C-SSRS "Since Last Visit" version should be administered at every study visit, including Visit 1

The instrument has been validated used successfully in adult patients with various psychiatric disorders that do not involve cognitive impairment. The C-SSRS outcomes that can be used for clinical management and safety monitoring are suicidal lethality rating, suicidal ideation score, and suicidal ideation intensity rating.

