3.2 Baseline Values

For all safety assessments, baseline will be defined as the last non-missing value prior to SPN-812 dosing in the 812P311 study.

For all efficacy assessments, subjects enrolled into $812P311 \le 7$ days after their last 812P306 visit, the "baseline" efficacy assessment is defined as the assessment that subject completed at Visit 2 in 812P306 prior to the first dose of SPN-812 in 812P306. Additionally, for subjects enrolled into 812P311 > 7 days after their last 812P306 visit, the baseline efficacy assessment is defined as the assessment that was completed at Visit 1 in 812P311 prior to the first dose SPN-812 in 812P311.

All post-baseline assessments are defined as any assessments that were completed after the first dose of SPN-812 in the 812P311 study.

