4.5.3 Laboratory Data

4.5.3.1 Potentially Clinically Significant Laboratory Values

The number and percentage of subjects with PCS values post-baseline will be summarized for the hematology and chemistry parameters defined in Table 1 and Table 2. All scheduled and unscheduled results will be included in this laboratory analysis.

Hematology parameter	Potentially clinically significant values
Hemoglobin	Female: <85 g/L or >160 g/dL)
	Male: <90 g/L or >170 g/L)
Hematocrit (HCT)	Hematocrit (Female) ≤32% or >49 %
	Hematocrit (Male) ≤37% or >48 %
Platelet count	<125 x 10^9/L or >470 10^9/L
White blood cells (WBC)	<2.0 x 10^9/L or >12.0 10^9/L
Basophils	>0.5 x 10^9/L
Eosinophils	>1.5 x 10^9/L
Lymphocytes	<0.5 x 10^9/L or >6.0 10^9/L
Monocytes	>1.6 x 10^9/L
Neutrophils	<1.5 x 10^9/L

Chemistry parameter	Potentially clinically significant values
Alanine aminotransferase	>3 x upper limit of normal (ULN)
(ALT)	
Albumin	<22 g/L or >65 g/L
Aspartate aminotransferase	>3 x ULN
(AST)	
Alkaline Phosphatase (ALP)	>3 x ULN
Bilirubin	>2 x ULN
Blood urea nitrogen (BUN)	>9.6 mmol/L
Calcium	<2.0 mmol/L or >2.75 mmol/L
Chloride	<90 mmol/L or >120 mmol/L
Creatinine	> 1.3 mg/dL or >115 µmol/L
Potassium	<3 mmol/L or >5.8 mmol/L
Sodium	<125 mmol/L or >158 mmol/L
Protein	<45 g/L
Glucose	non-fasting < 2.2 mmol/L or >8.9 mmol/L

Abnormally low or high laboratory results based on the laboratory normal ranges will be presented in a data listing.

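### SAP 4.5.6 counts a C-SSRS 'Yes' at any visit without a post-baseline limit, so pre-dose answers, mainly from Schedule B, can enter the count (minor)

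*SAP*

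**What the plan says.** SAP 4.5.6 presents the number and percentage of subjects with a 'Yes' "at any visit by categories for suicidal ideation only, suicidal behavior only, suicidality (ideation and behavior combined) items", and adds non-suicidal self-injurious behavior. Protocol 7.9 names the same three suicidality categories but sets no time window; the window comes from the SAP.

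SAP 3.2 supplies a definition that could have been used: "All post-baseline assessments are defined as any assessments that were completed after the first dose of SPN-812" in 812P311.

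Protocol 6.4, whose heading is about treatment-emergent ideation, gives the two stages of assessment different purposes. The initial evaluation is "conducted prior to enrollment to assess lifetime suicidal ideation" and to screen out subjects at risk. It is then "repeated at each subsequent study visit to monitor the occurrence of new suicidal and self-injurious tendencies". Under Protocol 6.4.1 the Baseline/Screening form is used only at Visit 'S' on Schedule B, and the Since Last Visit "version should be administered at every study visit, including Visit 1".

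SAP 5.1 lists one C-SSRS table (Table 9, by study visit) and SAP 5.2 one listing (Listing 9). The table shells in Appendix B were not available.

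**The concern.** An ever-'Yes' count in a long-term safety study will be read as describing the treatment period. As worded, it also takes in answers given before the first dose in this study, including lifetime history collected at screening. A subject who reports past ideation at Visit 'S' and never again would be counted with a subject who first reports ideation on SPN-812.

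Elsewhere the study keeps the two periods apart. Events before the first open-label dose go to medical history, not to the adverse event record (Protocol 5.1.1 and 6.3.3).

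The study has no control arm, and SAP 3.1 pools everyone under a single SPN-812 group. No comparison would therefore show that part of the percentage was pre-dose history.

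**Working it through.** There is no planned figure to reproduce: the documents give no C-SSRS rate, and Protocol 7.10 makes no sample size calculation. The check is mainly textual.

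**1. Is the limit missing only here?** Nearly, but not quite.

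| SAP section | Count | Post-baseline limit stated? |
|---|---|---|
| 4.5.3.1 | Laboratory values of potential clinical significance | Yes: "The number and percentage of subjects with PCS values post-baseline will be summarized" |
| 4.5.3.2 | Liver enzymes and function | Yes |
| 4.5.4 | Vital signs | Yes: "vital sign values postbaseline based on the normal ranges" |
| 4.5.5 | ECG heart rate, PR, QRS | Yes: "post-baseline abnormally low or high values for heart rate, PR interval, and QRS duration" |
| 4.5.5 | QT and QTcF categories | No |
| 4.5.6 | C-SSRS | No; any visit |

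**2. Do pre-dose C-SSRS records exist?** Yes, by design.
- Schedule B: the screening version at Visit 'S' (Protocol 5.1.1.2.1) and the Since Last Visit version at Visit 1 (5.1.1.2.2), the day dosing starts.
- Schedule A: one pre-dose record. Visit 1 uses the 812P306 end-of-study assessment, and the first open-label dose is taken the next morning (Protocol 3.1, 4.2).

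**3. Can a subject with a pre-dose 'Yes' be enrolled?**
- Schedule B: exclusion 24 covers an attempt, ideation at questions 4 or 5, or behavior, each within 6 months before screening, plus anyone the Investigator judges at significant risk. Ideation only at questions 1 to 3, or older ideation or behavior, is not excluded as such. The protocol states the lifetime scope for ideation; it does not say whether the form also records lifetime behavior.
- Schedule A: the effect should be small. No lifetime form is given, and exclusion 4 bars current suicidality. The Visit 1 record follows randomized treatment in 812P306, which was active drug for some subjects, so it is pre-dose for this study without being drug-free.

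**4. Direction.** Adding visits to an ever-'Yes' rule can add subjects but never remove them, so the any-'Yes' total can only rise. The 'only' rows behave differently if they are mutually exclusive:
- pre-dose ideation and nothing after dosing: enters 'ideation only' (row up);
- post-dose ideation and older pre-dose behavior: moves from 'ideation only' to the combined category (row down);
- pre-dose ideation and post-dose behavior: moves from 'behavior only' to the combined category (row down).

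**5. Size, as illustration only.** Excess in the any-'Yes' total = N × s × r, where N = 366 (maximum enrollment), s = share on Schedule B, and r = share of those with a pre-dose 'Yes' and no post-dose 'Yes'. Both s and r are assumed, Schedule A is taken to add nothing, and percentages are of 366.

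| s | N × s | r = 5% | r = 20% |
|---|---|---|---|
| 0% | 0 | 0 | 0 |
| 5% | 18.3 | 0.9 (0.25%) | 3.7 (1.0%) |
| 25% | 91.5 | 4.6 (1.25%) | 18.3 (5.0%) |

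**The case against.** The best defense is that the only planned C-SSRS table is by visit. If the SAP sentence just means a 'Yes' at a given visit, then Visit 'S' and Visit 1 have their own rows and nothing is mixed. The unavailable shells might show this. But the more natural reading of the sentence is a pooled ever-'Yes' count of subjects, and a table title does not narrow it. If the shells already restrict the count, the SAP text should say so.

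Several other points stand and limit the finding:
- A reader might infer that the C-SSRS count alone lacks the limit, or that the omission was deliberate. The QT/QTcF counts lack the same words, so the contrast is with most of the safety counts, not all.
- A reader might infer that the SAP contradicts the protocol. Protocol 7.9 sets no window, so it does not. Nor does SAP 4.5.6 call its count treatment-emergent; that expectation comes from Protocol 6.4.
- Suicidality recorded as an adverse event is summarized on a post-dose basis, because adverse events are collected only after the first open-label dose. That is a second view of the treatment period, though it leaves the C-SSRS count as it is.
- The endpoint is descriptive, with no test or decision rule, and Listing 9 gives the C-SSRS results for inspection.

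**Conclusion.** The point holds as a minor one. The stated rule admits pre-dose answers to a primary safety count, chiefly through Schedule B. The by-visit table and the listing make this detectable but do not correct it.

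Two stronger conclusions are tempting and unsupported. The first is that the distortion is upward throughout. That is certain for the any-'Yes' total only; the 'only' rows can rise or fall if the categories are exclusive, which the SAP does not settle. The second is that the inflation is material. The documents give neither the Schedule B share nor any pre-dose 'Yes' rate. Immediate rollover is the planned route, de novo entry waits on an IRB-approved note to file, and subjects who terminated 812P306 early need approval case by case. The true excess may be near zero, and the range of 0 to 18 subjects illustrated here rests wholly on assumed inputs. Because the any-'Yes' total cannot fall, the rule does not remove any subject with post-dose suicidality from it.

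The conclusion assumes the pooled reading of SAP 4.5.6 and that the shells do not already impose the limit.

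**What to change.** In SAP 4.5.6, replace the any-visit wording with 'at any post-baseline visit (as defined in Section 3.2)'. Show the Visit 'S' lifetime answers and the Visit 1 answers as separate pre-dose rows, and label Schedule A Visit 1 as the 812P306 end-of-study assessment so that it is not taken for drug-free history. The cost is one phrase and a few table rows from data already collected; nothing changes at the sites.
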